9.3.4.3 Continuous Endpoints

The analysis of the secondary endpoints related to PROs (B&B, NRS, and EHP-30), endocrine parameters (prolactin, TSH, and IGF-1), serum endometriosis biomarkers (VEGF, PIGF, IL-6, CA125, and sFlt-1), sizes of uterine fibroids (the sum of the size of all fibroids) assessed by MRI and TVU, will be described in this subsection.

The absolute value at baseline and the absolute value at each post baseline measurement, and the change from baseline to each post baseline measurement will be summarised. These endpoints will be analysed using a repeated measures ANCOVA model, with the change from baseline at each post-baseline time point as the dependent variable, the baseline value as a covariate, and the treatment group and treatment group by time as fixed effects. The error-covariance matrix will be unstructured. For the endpoints only measured once post baseline, an ordinary ANCOVA similar to the one used in the primary analysis will be applied (without imputations). The analyses will be performed for each of the three types of lesions, and for endometriosis (endometrioma and DIE). The treatment difference between active treatment versus placebo will be reported with 95% confidence interval and corresponding p-value for each post baseline of these endpoints.

As an additional analysis the menstrual bleeding pattern will be investigated by analysing the number days with menstrual bleeding (calculated as the stop date of menstrual bleeding minus start day plus 1) for each of the four cycles under treatment and the length of the menstrual cycle (calculated as the difference between two consecutive start of menstrual bleeding dates) for each of the four cycles under treatment. The baseline values for these two variables will be the number of bleeding days and the length of the menstrual period of the last pre-treatment cycle, respectively. If the stop date of a menstrual bleeding is missing due to the subject still bleeding at the RM+7 visit, the visit date plus 1 is used for calculating the length of the bleeding period. If the start date of menstrual bleeding is missing due to the subject having delayed or skipped menstrual bleeding, both of the two length of menstrual cycles will be considered missing, and the length of the bleeding period will be set to 0. To summarise the occurrence of delayed or skipped menstrual bleeding descriptive tables summarising the number of delayed or skipped menstrual bleedings and the number of subjects that experience at least one delayed or skipped menstrual bleeding will be prepared.

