7.2 Assessments Related to Secondary Endpoints

7.2.1 Transvaginal Ultrasound (TVU)

Transvaginal ultrasound (TVU) will be performed, preferably by the same sonographer, at the screening visit and at end-of-treatment / cycle 4.

One purpose of TVU is to assess the general health status of uterus, endometrium and ovaries in order to identify any abnormal findings. The other purpose of TVU is to evaluate endometrial thickness, number and size of endometrioma if presented, number and size of fibroids if presented as well as number and size of ovarian cysts if presented.

Endometrial thickness (composed of both layers of the endometrium) will be measured in the sagittal view of the uterus from the proximal and distal interfaces between the echogenic

endometrium and the hypoechoic inner layer of the myometrium. Care should be taken not to include the presence of any fluid in the uterine cavity in calculating the endometrial thickness value. Endometrial thickness will be recorded in mm.

Endometrioma and/or fibroids will be recorded as observed or not. If observed, the number and size of endometrioma and/or fibroids should be recorded.

Ovarian cysts will also be recorded as observed or not. If observed, the number and size of ovarian cysts should be recorded.

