9.6 Endpoint Assessments

9.6.1 General Considerations

The primary analysis of the primary endpoint will be based on the FAS population, while the analysis of the primary endpoint based on the PP population will be considered supportive and serve as one of the sensitivity analyses.

The analysis of all the secondary and exploratory endpoints except the safety endpoints (i.e. adverse events, clinical chemistry and haematology parameters) will be performed for the FAS population. The safety endpoints will be analysed for the safety analysis set unless otherwise noted.

Statistical tests will be performed using a two-sided test at a 5% significance level. Treatment differences will, where appropriate, be presented with 95% confidence intervals and p-values corresponding to the statistical test of the hypothesis of “equal effect” against the alternative of “different effect”.

Continuous variables will be presented with number of subjects, mean, standard deviation, median, inter-quartile range, minimum, and maximum. Categorical variables will be presented with number and percentage of subjects within each specific category.

Missing Data

Missing data from the MRI

If a subject is prematurely discontinued during or after cycle 2, an end-of-treatment MRI examination will be performed. The results from this end-of-treatment MRI will be used.

If the end-of-treatment MRI examination is not performed or is missing, the missing measurement will be imputed using a multiple imputation strategy. The imputation will be based on a missing-at-random assumption using baseline MRI results and some other measurements. The precise imputation strategy will be described in the SAP.

Missing data for adverse events

For adverse events, missing values will be treated as missing, except for causality, intensity, seriousness and outcome of adverse events, where a worst-case approach will be used.

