9.6.2 Primary Endpoint

For each type of lesion (endometrioma, DIE and adenomyosis), the primary endpoint is the change in the sum of the lesion sizes at cycle 4, i.e. the difference between the active treatment group and the placebo group in the change from baseline in the sum of the lesion sizes of the same type at the end of cycle 4. The baseline is defined as the sum of the sizes of all lesions of the same type ≥ 10 mm obtained from the MRI examination at screening. At end-of-treatment / cycle 4, the sizes of all lesions included at baseline of the same type will be summed. For each type of lesions, subjects with at least one lesion of that type ≥ 10 mm at baseline will be included.

For each type of lesions, the primary endpoint will be analysed using an analysis of covariance (ANCOVA) model, with the change in the sum of lesion sizes from baseline measured at cycle 4 as the dependent variable, the baseline sum of lesions as covariate, the treatment group and site as fixed effect. The treatment difference between active treatment versus placebo will be reported with 95% confidence interval and corresponding p-value for each of the three types of lesions:

$$\begin{cases} H_0^{P1} : \mu_{QVR}^1 = \mu_{Placebo}^1 \\ H_1^{P1} : \mu_{QVR}^1 \neq \mu_{Placebo}^1 \end{cases}$$

$$\begin{cases} H_0^{P2} : \mu_{QVR}^2 = \mu_{Placebo}^2 \\ H_1^{P2} : \mu_{QVR}^2 \neq \mu_{Placebo}^2 \end{cases}$$

$$\begin{cases} H_0^{P3} : \mu_{QVR}^3 = \mu_{Placebo}^3 \\ H_1^{P3} : \mu_{QVR}^3 \neq \mu_{Placebo}^3 \end{cases}$$

Where (H_0^{P1}) , (H_0^{P2}) , (H_0^{P3}) are the null hypotheses for each of the 3 types of lesions, (H_1^{P1}) , (H_1^{P2}) , (H_1^{P3}) are the alternative hypotheses for each of the 3 types of lesions, and

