9.6.4 Exploratory Endpoints

The exploratory endpoints related to the MRI-derived perfusion and diffusion imaging biomarkers will be analysed by the central imaging laboratory and will be reported separately.

Changes in the sizes of uterine fibroids assessed by MRI / TVU and changes in the plasma and serum endometriosis biomarkers will be analysed in a similar way as the primary endpoint but without sensitivity analyses.

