9.3 Secondary and Exploratory Endpoints

The summaries and analysis of the secondary efficacy endpoints will be performed for the FAS. No sensitivity analysis will be performed for any of the secondary or exploratory outcomes.

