9.3.4 Other Secondary and Exploratory Endpoints

All summaries in this section will be performed by treatment and in total. As indicated in [Table 9-1](#) some endpoints will be summarised and analysed for each of the three types of lesion (endometrioma, DIE and adenomyosis) and for endometriosis (endometrioma and DIE), some for all types of lesion combined, and some for both.

No imputation will be done for the analysis of these other secondary and exploratory endpoints. The endpoint derived from the MRI will, however, use the end-of-treatment assessment even if the end-of-treatment assessment is performed before end of cycle 4.

Table 9-1 Analyses of Other Secondary and Exploratory Endpoints

Endpoint	Analysis method					Presentation	
	ANCOVA	Repeated measures ANCOVA	Logistic regression	Negative Binomial regression	Proportional odds	By type of lesion and disease	All types of lesions combined
Proportion of lesions by type with a decrease in a size of ≥ 5 mm on MR images at cycle 4			X			X	
Proportion of subjects with a lesion of any type decreased in a size of ≥ 5 mm on MR images at cycle 4			X				X
Number of new endometrioma, DIE and adenomyosis lesions by type on MR images at cycle 4				X		X	
Number of disappearing endometrioma, DIE and adenomyosis lesions by type on MR images at cycle 4				X		X	
Changes in the total physical sign pain score and change in the total symptom and sign severity score of the Biberoglu and Behrman (B&B) scale at cycle 4	X					X	X
Changes in the Numerical Rating Scale (NRS) pain scores at cycles 1, 2, 3 and 4		X				X	X
Changes in each of the five EHP-30 scores and the total EHP-30 score per cycle at cycles 2 and 4		X				X	X
Changes in the menstrual bleeding pattern over 4 cycles		X			X	X	X
Change in serum levels of prolactin, TSH, IGF-1 during cycle 1, at cycles 2 and 4		X				X	X
Changes in the sizes of uterine fibroids on MR images at cycle 4	X						
Changes in the sizes of uterine fibroids assessed by TVU at cycle 4	X						
Changes in circulating levels of VEGF, PIGF, IL-6, CA125 and sFlt-1 at cycle 4	X					X	X

Note: Exploratory endpoints are shaded in grey.

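### The fibroid ANCOVAs are specified only within endometriosis/adenomyosis lesion-type sets, with no stated fibroid population and no pooled model, which costs precision for a question that does not depend on lesion type

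*SAP*

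**What the plan says.** - **Objective.** SAP 2.1.3 and Protocol 2.1 set a separate exploratory objective: the ring's effect on fibroid size by MRI and by TVU. Lesion type is not part of it.
- **Endpoint and grouping.** SAP 9.3.4.3 handles "sizes of uterine fibroids (the sum of the size of all fibroids) assessed by MRI and TVU" together with PROs, hormones and serum biomarkers. For all of them it states: "The analyses will be performed for each of the three types of lesions, and for endometriosis (endometrioma and DIE". It mentions no model with all lesion types combined.
- **Table 9-1.** SAP 9.3.4 uses this table to show which endpoints are presented by type, combined, or both. The row "Changes in the sizes of uterine fibroids on MR images at cycle 4" and the matching TVU row have ANCOVA marked but, in the text available, no presentation mark. The other continuous endpoints in the table are marked for both.
- **Analysis set.** Protocol 9.6.1 assigns to the FAS "The analysis of all the secondary and exploratory endpoints except the safety endpoints". SAP 9.3 says "The summaries and analysis of the secondary efficacy endpoints will be performed for the FAS". The five full analysis sets in SAP 6.1 are defined by endometrioma, DIE and adenomyosis, or as all treated subjects. None refers to fibroids.
- **Analogy with the primary endpoint.** Protocol 9.6.4 says that fibroid changes "will be analysed in a similar way as the primary endpoint but without sensitivity analyses". For the primary endpoint, Protocol 9.6.2 says "For each type of lesions, subjects with at least one lesion of that type ≥ 10 mm at baseline will be included", and sums at end of treatment only the lesions counted at baseline.
- **Recording and missing values.** For TVU, Protocol 7.2.1 says "If observed, the number and size of endometrioma and/or fibroids should be recorded". SAP 9.3.4 rules out imputation for these endpoints.

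**The concern.** Fibroids are incidental here. Inclusion criterion 7 neither requires nor excludes them, apart from submucosal ones. Whether a woman also has endometrioma, DIE or adenomyosis does not form part of the fibroid question, yet the text sorts the fibroid analysis by exactly that trait. Read literally, each modality gets four models in overlapping sets and none that uses every woman who can inform the answer.

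Two further choices are left to whoever programs the analysis: whether a woman with no baseline fibroid is left out or entered as 0, and whether a fibroid first seen at end of treatment counts in the sum of all fibroids. The first changes what the estimate in mm means. At stake is whether an exploratory result is usable and interpretable, not any primary or secondary conclusion.

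**Working it through.** **1. The plan's own figure.** The documents give no power for fibroids, so the method is first checked on the primary endpoint (SAP 3.3): difference 6 mm, SD 4.5 mm, 16 versus 8, two-sided 5%.

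Noncentrality = δ / [σ √(1/n₁ + 1/n₂)] = 6 / [4.5 × √(1/16 + 1/8)] = 6 / 1.949 = 3.08, with 22 df. The noncentral t gives 83.7%; the plan states 83%. The same formula reproduces every cell of SAP Table 3-2.

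**2. Inputs for fibroids.** From the documents: 72 women planned, 24 per sub-group, and 1:1 allocation as actually used (SAP 3.3). Assumed, because the documents are silent: 20, 30 or 40% of women with fibroids; mean fibroid sum 30 mm; 20% shrinkage on active treatment and none on placebo; noise equal to 15% of baseline. At the mean this is an effect of 0.20 × 30 = 6 mm and an SD of 0.15 × 30 = 4.5 mm.

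**3. Effect of restricting to a lesion type (t-test, women with fibroids only).** At a 30% share:
- Pooled: 0.30 × 36 = 10.8, about 11 per arm. Noncentrality 6 / [4.5 × √(2/11)] = 3.13, 20 df, power 84%.
- One set of 24: 0.30 × 12 = 3.6, about 4 per arm. Noncentrality 6 / [4.5 × √(2/4)] = 1.89, 6 df, power 36%.
- If overlap doubled the set to 48: 0.30 × 24 = 7.2, about 7 per arm. Noncentrality 6 / [4.5 × √(2/7)] = 2.49, 12 df, power 63%.

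For 24 against 72 women the standard error is larger by about √3 = 1.7.

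**4. ANCOVA simulation.** Change on treatment and baseline, 3,000 trials per cell, 1:1. It was run twice, with the SD of the baseline sum assumed to be 12 mm and then 10 mm. Power at fibroid shares of 20/30/40%:

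| Set | Women without a fibroid | SD 12 mm | SD 10 mm |
|---|---|---|---|
| 24 | left out | 9/19/32% | 11/20/33% |
| 24 | entered as 0 | 7/19/32% | 9/20/33% |
| 72 | left out | 50/74/86% | 54/75/88% |
| 72 | entered as 0 | 52/75/88% | 55/77/89% |

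These are lower than the t-test figures because the baseline covariate uses a degree of freedom and the number of women with fibroids varies by chance.

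**5. Separating the two mechanisms.** Reading down the table, moving from 24 to 72 women changes power greatly; moving from left out to 0 changes it by about 2 points at most. The estimate behaves the other way. With fibroid women only it is about -6 mm in either set. With zeros it is -1.0/-1.6/-2.3 mm in 24 women and -1.1/-1.7/-2.4 mm in 72, roughly the fibroid share times 6 mm (1.2/1.8/2.4). Zeros shrink the residual variance along with the effect, so the test statistic barely moves.

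**The case against.** The strongest reply is that the plan can be read sensibly as it stands. The by-type sentence in SAP 9.3.4.3 is generic and closes a paragraph covering many endpoints. The blank cells in Table 9-1 may mean that the authors did not intend by-type presentation, or marks may have been lost when the document was converted to text. SAP 9.1 also promises descriptive summaries of all efficacy endpoints for the types combined.

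Part of this stands. The blank cells alone prove nothing and should be checked against the original table. But if they are real, the table does not say which grouping applies; if marks were lost, the text of 9.3.4.3 still names only by-type models. A combined descriptive summary is not a combined treatment comparison.

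A reader might go further and infer that women without fibroids enter with a sum of 0 and so dilute the effect and its power. The documents do not support that. No passage assigns such a value. TVU size is recorded only when a fibroid is seen, no imputation is done, and the analogy with the primary endpoint points to requiring a baseline fibroid. Where the SAP wants a zero it says so, as for an undetectable lesion in 9.2.1 or a skipped bleed in 9.3.4.3. And zeros, if used, would cost almost no power.

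It would also be wrong to speak of a few women with fibroids being split between types. Prevalence is not given, and SAP 3.2 allows one woman to be in several lesion-type analyses.

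Finally, the endpoint is exploratory, with no sample-size basis, so power is only a convenient measure of precision here.

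**Conclusion.** The point holds as a minor one. The only grouping stated for the fibroid ANCOVAs is by lesion type and for endometriosis. Table 9-1 as available does not settle the presentation, and no passage defines who enters or what value a woman without a fibroid has.

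Under the assumed inputs, women with fibroids give about 10/20/33% power in one set of 24, against about 50-54/75/87% pooled over 72. The size of the gap depends on assumed prevalence, effect and noise. It narrows where overlap makes a lesion-type set larger, or in the combined endometriosis set; with 48 women and a 30% share, the t-test comparison is 63% against 84%.

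The missing rule for women without a fibroid is a separate matter of interpretation: it could scale the estimate down to roughly the fibroid share, but it is not the source of the power loss.

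**What to change.** In SAP 9.3.4.3, state that each fibroid ANCOVA (one for MRI, one for TVU) is run once as the main fibroid analysis, in combined-FAS women with at least one baseline fibroid by that modality. Sum the fibroids present at baseline, in line with Protocol 9.6.4 and 9.6.2, and report new fibroids separately. State that women without a baseline fibroid are not in the model. In Table 9-1, mark the column for all lesion types combined in both fibroid rows. Drop the by-lesion-type fibroid models, or keep them as descriptive summaries only.

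The cost is SAP wording, to be settled before unblinding. It needs no new data and leaves fewer models to run. What is given up is a formal by-type fibroid comparison, for which the documents state no purpose.

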7.2.3 Numerical Rating Scale (NRS)

NRS is a self-administered 11-point pain scale, with 0 indicating no pain and 10 indicating worst imaginable pain. At each RM+7 visits from randomisation to end-of-treatment / cycle 4, subjects will be asked to score the worst pain in relation to endometriosis / adenomyosis on the NRS based on a recall of their experiences during the following timeframes:

- during the last menstrual cycle
- during the menstrual period of the last menstrual cycle
- during the non-menstrual period of the last menstrual cycle

The NRS will be completed by subjects on paper prior to ring insertion at randomisation and prior to other non-PRO procedures at each RM+7 visit from cycle 1 to end-of-treatment / cycle 4. The responses must be reviewed for legibility and completeness by the trial coordinator before the subject leaves the clinic. The scores obtained at randomisation will be used as baseline.

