7.4.3 Menstrual History

Information about the menstrual history (average cycle length, average number of days with

menstrual bleeding and amount of menstrual flow) will be obtained at screening. In addition, the start and stop dates (if available) of the immediate past menstrual period should be noted. Any history of irregular vaginal bleeding outside menstrual period will also be recorded.

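### The SAP words the baseline for menstrual cycle length as the length of the menstrual period; this is probably a slip for 'cycle', but if programmed as written it gives cycle length a bleeding-duration baseline

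*SAP*

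**What the plan says.** The last paragraph of SAP section 9.3.4.3 adds an analysis of menstrual bleeding pattern with two variables, each derived for the four cycles under treatment:

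- Days of bleeding, "calculated as the stop date of menstrual bleeding minus start day plus 1".
- Menstrual cycle length, "calculated as the difference between two consecutive start of menstrual bleeding dates".

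It then gives both baselines in one sentence: they "will be the number of bleeding days and the length of the menstrual period of the last pre-treatment cycle", followed by the word 'respectively'. That final word pairs the first baseline with bleeding days and the second with cycle length.

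The preceding paragraph of the same section says how continuous endpoints are handled. Baseline, post-baseline values and change are summarised. Endpoints measured repeatedly are analysed by repeated measures ANCOVA on change, with baseline as a covariate. SAP Table 9-1 appears to mark that model for menstrual bleeding pattern.

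**The concern.** The post-baseline variable runs from one bleeding start to the next, while the quantity named as its baseline is, in the trial's own vocabulary, the bleed alone. A change from baseline has meaning only if both values measure the same thing. Followed to the letter, the sentence would give both variables a bleeding-duration baseline and leave cycle length without one of its own.

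Two outputs would suffer: the table of change in cycle length, and the precision of the model that compares the arms. Menstrual bleeding pattern is a secondary objective, and the groups by lesion type are small (about 24 planned per sub-group), so avoidable loss of precision is worth preventing.

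**Working it through.** The plan states no figure on this point, so there is none to reproduce. The check has three parts.

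**1. What 'menstrual period' means in the documents**

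- Protocol section 7.2.3 asks for worst pain "during the menstrual period of the last menstrual cycle" and, separately, for the non-menstrual part of that cycle. The period is therefore a part of the cycle.
- Protocol section 7.4.3 says that "the start and stop dates (if available) of the immediate past menstrual period should be noted". A start and a stop date describe a bleed.
- Protocol section 7.2.5 likewise ties the term to the start, stop and amount of bleeding.
- SAP section 5 defines the non-menstrual period as the interval between the end of one bleed and the start of the next.

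Read this way, the second baseline is the duration of the bleed.

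**2. Change from baseline under the literal reading**

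Formula: spurious change = cycle length − bleeding days, when nothing has truly changed.

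Inputs: the eligible cycle length is 24 to 35 days (Protocol section 4.1.1, criterion 4). The documents do not give bleed length; 5 days is assumed, with a range of 3 to 7.

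| Cycle (days) | Bleed 3 | Bleed 5 | Bleed 7 |
|---|---|---|---|
| 24 | 21 | 19 | 17 |
| 28 | 25 | 23 | 21 |
| 35 | 32 | 30 | 28 |

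The typical case is 28 − 5 = 23 days, with a range of 17 to 32. It would appear in both arms. With the pre-treatment cycle as baseline, the same case gives 28 − 28 = 0.

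**3. Effect on the ANCOVA**

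Write Y for on-treatment cycle length, B for whatever is used as baseline, and T for treatment.

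- The model Y − B = a + τT + βB can be rearranged as Y = a + τT + (β + 1)B. The estimate of τ is therefore the same whether change or the raw value is analysed. Because B is measured before randomised treatment starts, τ is unbiased with either baseline.
- With the woman's own pre-treatment cycle length as B, the residual variance is σ²(1 − ρ²), where ρ is the correlation between her pre-treatment and on-treatment cycle lengths.
- With bleeding days as B, assumed uncorrelated with cycle length, the residual variance stays at σ².
- The variance ratio, literal to intended, is therefore 1/(1 − ρ²).

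| ρ (assumed) | 1/(1 − ρ²) | Rise in variance | SE ratio, formula | SE ratio, simulated |
|---|---|---|---|---|
| 0.3 | 1/0.91 = 1.10 | 10% | 1.05 | 1.05 |
| 0.5 | 1/0.75 = 1.33 | 33% | 1.15 | 1.15 |
| 0.7 | 1/0.51 = 1.96 | 96% | 1.40 | 1.40 |

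The simulation used 12 women per arm, one post-baseline time point, no treatment effect and 4,000 runs. It assumed cycle length with mean 28 and SD 2.5 days, and bleeding with mean 5 and SD 1.2 days. The mean estimated treatment difference was within 0.03 days of zero under both baselines. The mean change was about 23 days under the literal baseline and about 0 under the intended one.

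**The case against.** The strongest reply is that this is one wrong word, not a choice of analysis. Bleeding days already have their own baseline in the same sentence, so the literal reading names one quantity twice and defeats the pairing. Soon afterwards the SAP calls the bleed something else: "the visit date plus 1 is used for calculating the length of the bleeding period". A programmer would probably read 'cycle'. A baseline near 5 days printed beside on-treatment values near 28 would also be hard to miss in review. All of this stands, and it makes the point minor and conditional.

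A reader might go further than the documents allow in three ways.

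- *That the reported result will show cycles lengthening by about three weeks.* This needs literal programming and an unnoticed table; the documents do not show that either will happen.
- *That the comparison between arms would be biased.* It would not; only precision is lost.
- *That the trial's evidence on menstrual effects, or a non-hormonal claim, rests on this sentence.* The stated objective is menstrual bleeding pattern. Its main analysis, the first change in amount of flow (SAP section 9.3.4.1), does not use this baseline, nor do the tables of delayed or skipped bleeding. The statement that menstrual cyclicity is unaffected, in Protocol section 1.2, is a phase 1 result. No passage makes this cycle-length analysis carry a claim.

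The reply does not remove the need for a correction. No text states the intended baseline, and changing one word leaves room for doubt. SAP section 3.1 defines a cycle from day 7 after one return of menses to day 7 after the next, this paragraph measures start to start, and the menstrual history also records an average cycle length.

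**Conclusion.** The point holds as a wording error in operative analysis text, most likely a slip. Followed as written, it would give cycle length the wrong baseline. The consequences, all conditional on literal programming, are:

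- a spurious mean change of about 23 days in both arms, resting on an assumed 28-day cycle and 5-day bleed;
- a loss of precision that depends on correlations the documents do not give, and on bleeding days being unrelated to cycle length;
- no bias in the treatment difference.

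The reach is one additional analysis of a secondary endpoint. The primary analysis is untouched.

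**What to change.** In SAP section 9.3.4.3, replace the second baseline with: *the length of the last pre-treatment menstrual cycle, calculated as the bleeding start date reported at visit 2 minus the bleeding start date reported at visit 1*. Naming the two dates matches the start-to-start definition used on treatment and closes off the other readings of cycle length.

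Add that the baseline is missing when either date is unavailable. This is needed because both dates are collected only where available: the visit 1 date comes from the menstrual history (Protocol section 7.4.3) and the visit 2 date from the bleeding-pattern inquiry (Protocol sections 6.2.3 and 7.2.5).

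The cost is one revised SAP sentence and a short rule for missing dates. It needs no new data and no change to any other analysis. The price of the missing-date rule is that women without both dates drop out of the change-from-baseline analysis of cycle length.
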